### 3.9.1.3 TEAEs during OL Treatment Period

TEAE for the OL treatment period will be defined as any AE with onset on or after the administration of the first open-label SC dose of MEDI2070 up to and including 28 weeks post-last dose. Similar tabular summaries will be prepared for the OL treatment period using the OL population.

### 3.9.2 Adverse Events of Special Interest (AESI)

An AESI is one of scientific and medical interest specific to understanding of the investigational product and requires close monitoring and rapid communication by the investigator to the sponsor. An AESI may be serious or non-serious. Identification of TESIS through search criteria (Standardized MedDRA Query (SMQ) etc.) will be an ongoing task throughout the study and latest convention will be used to summarize by SOC and PT in each category. In particular, the time to onset of surgery for CD complications will be summarized for each treatment group.

[figure not shown]
**Table 3.9.2-1 AESIs Categories**

AESI Category	Description
Hepatic Function Abnormality (Hy's Law)	The Hy's law is defined in the protocol Section 5.6.2. AEs meeting the Hy's law criteria will be identified using MedDRA SMQ.
Infusion/injection site Reactions	AEs with PT "infusion reaction" will be captured under this category.
Infections	An event recorded on the AEs eCRF that is coded to the MedDRA SOC of "Infections and Infestations."
Systemic Hypersensitivity	e.g. anaphylaxis
Malignancies	
Major Cardiac Events (MACE)	AEs defined as myocardial infarction, stroke, or cardiovascular death
Ocular AEs	Including cataracts

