## 2.2.4 Safety Endpoints

1. Incidence and severity of TEAEs
2. Incidence of TESAEs
3. Incidence and severity of treatment-emergent AESIs, including:
  - a. Incidence and severity of infusion/injection-site reactions
  - b. Incidence and severity of hypersensitivity reactions
  - c. Incidence of malignancies
  - d. Major cardiac events, defined as myocardial infarction, stroke, or cardiovascular death
  - e. Incidence and severity of ocular AEs, including cataracts
4. Incidence of AEs leading to investigational product discontinuation
5. Incidence of specific laboratory abnormalities

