### Injection-Site Reactions

The site of injection will be assessed at every visit at which there is an SC injection through the end of the open-label period. Injection-site reactions will be recorded as AEs according to the criteria described in Section 5.4.

[REDACTED]

[REDACTED]

[REDACTED]

[REDACTED]

[REDACTED]

[REDACTED]

[REDACTED]

[REDACTED]

[REDACTED]

[REDACTED]

[REDACTED]

[REDACTED]

[REDACTED]

[REDACTED]

[REDACTED]

[REDACTED]

[REDACTED]

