### **5.6.2 Hepatic Function Abnormality**

Cases where a subject shows elevations in liver biochemistry may require further evaluation and occurrences of AST or ALT  $\geq 3 \times$  ULN together with total bilirubin  $\geq 2 \times$  ULN may need to be reported as SAEs. Please refer to Appendix 4 for further instruction on cases of increases in liver biochemistry and evaluation of Hy's Law.

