#### **3.8.1.2 Treatment-Emergent AEs during DB Treatment Period**

For subjects entering the OL treatment period, the TEAE will be defined as any AE with onset on or after the administration of the first dose of blinded investigational product up to the day prior to administration of the first OL SC dose. For subjects not entering the OL treatment period, the TEAE will be defined as any AE with onset on or after the administration of the first dose of blinded investigational product up to and including 28 weeks post last blinded dose.

All TEAEs including TESAEs, Adverse Event of Special Interest (AESIs), and TEAEs leading to permanent discontinuation of investigational product will be summarized overall. The TEAEs with severity grades will be summarized by grades assigned by National Cancer Institute Common Terminology Criteria for AEs (NCI CTCAE) V4.0. Tabular summaries of the TEAEs during the DB treatment period will be provided as follows:

- Incidence rate of TEAEs by SOC and PT
- Incidence rate of TEAEs by SOC, PT, and severity
- Incidence rate of related TEAE by SOC and PT
- Incidence rate of TESIs by SOC and PT

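### The original SAP's AESI category for infusion/injection-site reactions is captured by one infusion term only, so injection-site reactions fall outside the category

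*Combined protocol and SAP*

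**What the plan says.** **Endpoint.** Protocol Section 2.2.4, item 3a, lists "Incidence and severity of infusion/injection-site reactions" among the treatment-emergent AESIs. Section 4.8.5.1 plans the frequency of these reactions for each arm.

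**Collection.** The injection-site paragraph of protocol Section 4.3 has the site assessed at every visit with an SC injection through the end of the open-label period. It states that "Injection-site reactions will be recorded as AEs".

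**Capture rule.** In original SAP Table 3.9.2-1 the category is called 'Infusion/injection site Reactions'. The description beside it says that AEs with the preferred term 'infusion reaction' "will be captured under this category". It names no other term.

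**AESI definition in the protocol.** Sections 5.3.1 to 5.3.3 list Hy's law, infusion reactions, malignancies, hypersensitivity, ocular AEs and major cardiac events. Injection-site reactions are not listed there.

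**Final SAP.** The SAP written after early termination keeps a double-blind table of "Incidence rate of TESIs by SOC and PT" (Section 3.8.1.2). Its visible text has no table of AESI categories and no search rule.

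**The concern.** The category's name matches the endpoint, but its rule retrieves only the infusion half. A table run to that rule would carry both reaction types in its title and count one. A reader comparing arms could take a low figure as evidence of good local tolerability of the SC injection, when injection-site events had never been eligible for the count.

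The rule is narrow even for infusions. Protocol Sections 5.3.2 and 5.4.3.1 use both 'infusion reaction' and 'infusion-related reaction', and the SAP names only the first.

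**Working it through.** The plan states no figure on this point, so the check is of the text, plus a count of dosing occasions.

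**1. Endpoint against rule**
- Required: infusion reactions and injection-site reactions, with incidence and severity (protocol 2.2.4, item 3a) and frequency by arm (4.8.5.1).
- Recorded: injection-site reactions, as AEs (protocol 4.3). The events are therefore in the AE data and available to a search.
- Retrieved by Table 3.9.2-1: the preferred term 'infusion reaction'. Injection-site terms retrieved: none.

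**2. Can the general TEAE tables supply the category figure?**
- Original SAP Section 3.9.1 counts each specific event once per subject, and Section 3.9.1.2 tabulates TEAEs by SOC and preferred term.
- Take a subject with two different injection-site preferred terms. The subject adds 1 to each of two rows, so the rows sum to 2, while the correct category count is 1.
- Adding preferred-term rows therefore overstates the number of subjects whenever terms overlap. The category incidence has to be derived at subject level from a term list.

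**3. Exposure by route** (treatment regimen table, protocol Table 3.1.2-1; the same in all five arms because of the placebo SC and IV administrations)
- Double-blind SC: Weeks 0, 4, 8, 12, 16, 20, 24 = 7 visits. Double-blind IV: Weeks 0 and 4 = 2 visits.
- Open-label SC: Weeks 28, 32, 36, 40, 44, 48 = 6 visits. Open-label IV: 0.
- Total: 7 + 6 = 13 visits, all with an SC injection; 2 with an infusion.
- SC share of route occasions: 13 / (13 + 2) = 87% overall; 7 / (7 + 2) = 78% in the double-blind period.

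**4. Size**
- The documents give no reaction rate for either route. As an assumption only, suppose 2% to 10% of subjects have an injection-site reaction.
- Planned trial: 342 × 0.02 = 6.8 to 342 × 0.10 = 34.2 subjects outside the category.
- Trial as terminated: 29 × 0.02 = 0.6 to 29 × 0.10 = 2.9 subjects.
- This shows scale under an assumed rate and is not an estimate.

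**The case against.** **The table is not a full search specification.** Its column is headed as a description, some entries are only examples, and the malignancy entry is blank. Original SAP Section 3.9.2 says that searching for these events continues through the study and that the most recent convention will apply. Section 1 places detailed specifications in a separate programming plan, which is not available here. This stands in part: the rule is not locked, and a later convention may have widened it. But the infusion row is worded as a rule, and neither general statement supplies a different one.

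**No event disappears.** This stands. The original SAP tabulates TEAEs by SOC and preferred term. The final SAP also tabulates them by severity and lists every AE. A reader might infer that injection-site reactions are lost from the safety report; the documents do not support that. They are absent from the AESI category only.

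**The 2-of-13 count is not an under-count.** This stands too. It counts routes, not reactions, and 6 of the 13 visits belong to an optional open-label period without a control. It shows only that the omitted half is the route used throughout.

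**Hy's law.** The same table points to protocol Section 5.6.2 and says that AEs meeting Hy's "law criteria will be identified using MedDRA SMQ". Section 5.6.2 gives laboratory thresholds: AST or ALT at least 3 × ULN "together with total bilirubin" at least 2 × ULN. A reader might infer that laboratory Hy's law cases are missed, because a query of AE terms cannot check laboratory values. That is not shown, for three reasons:
- Under protocol Appendix 4, the thresholds alone define only Potential Hy's Law. Hy's Law also requires that no other cause be found.
- Appendix 4 has confirmed cases, and cases still unresolved after 3 weeks, reported as SAEs under named terms, so they enter the AE data.
- The parts of both SAPs where a laboratory tabulation could sit are redacted, and protocol Section 4.8.5.2 already plans grouped hepatic summaries.

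What remains is that capture through AE terms depends on the investigator recognising and reporting the case.

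**Conclusion.** The point holds for injection-site reactions. Read literally, the only stated capture rule excludes half of what the category's own name and protocol endpoint 3a cover. This is a wrong rule rather than missing detail, and it affects the category-level incidence and severity, not the collection of data.

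No size can be put on the under-count without an external reaction rate. With 29 subjects randomized, no statistical safety comparisons planned and all data listed, the absolute effect in the final report is likely to be small. It would have mattered more at the planned 342.

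The conclusion assumes that the table was applied as written and that the programming plan did not override it. For the final SAP, it rests on the visible text showing no AESI definition; redaction prevents certainty.

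The protocol shares the inconsistency: its endpoint treats injection-site reactions as AESIs and its Section 5.3 does not. Changing the SAP row alone would leave that open.

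**What to change.** - **Original SAP Table 3.9.2-1:** replace the single preferred term with a MedDRA term list for the category that covers infusion-related and injection-site reactions. Have the sponsor review it and fix it before unblinding. Count each subject once in the category, and once by worst severity.
- **Final SAP Section 3.8.1.2:** use the same definition for the retained treatment-emergent AESI table, and state it there or by reference.
- **Protocol Section 5.3 and endpoint 3a:** reconcile whether injection-site reactions are AESIs.
- **Hy's law, optional:** list subjects who meet the laboratory thresholds as Potential Hy's Law, beside cases reported as 'Hy's Law' or 'Potential Hy's Law'. If the redacted laboratory section already does this, a cross-reference is enough. Cases found by thresholds alone should not be labelled Hy's law, because Appendix 4 excludes those with another explanation.

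The cost is a term list and a few sentences of wording. The reactions are already recorded as AEs, so the main change needs no new data.

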### 3.9.3 Deaths and Treatment Discontinuations due to Adverse Events

Deaths and treatment discontinuation due to AEs will be listed and summarized by treatment groups.

[Redacted text]

[Redacted text]

[Redacted]	[Redacted]	[Redacted]
[Redacted]	[Redacted]	[Redacted]
[Redacted]	[Redacted]	[Redacted]
[Redacted]	[Redacted]	[Redacted]
[Redacted]	[Redacted]	[Redacted]
[Redacted]	[Redacted]	[Redacted]
[Redacted]	[Redacted]	[Redacted]
[Redacted]	[Redacted]	[Redacted]
[Redacted]	[Redacted]	[Redacted]
[Redacted]	[Redacted]	[Redacted]
[Redacted]	[Redacted]	[Redacted]
[Redacted]	[Redacted]	[Redacted]
[Redacted]	[Redacted]	[Redacted]
[Redacted]	[Redacted]	[Redacted]
[Redacted]	[Redacted]	[Redacted]
[Redacted]	[Redacted]	[Redacted]
[Redacted]	[Redacted]	[Redacted]
[Redacted]	[Redacted]	[Redacted]
[Redacted]	[Redacted]	[Redacted]
[Redacted]	[Redacted]	[Redacted]
[Redacted]	[Redacted]	[Redacted]
[Redacted]	[Redacted]	[Redacted]
[Redacted]	[Redacted]	[Redacted]
[Redacted]	[Redacted]	[Redacted]
[Redacted]	[Redacted]	[Redacted]
[Redacted]	[Redacted]	[Redacted]
[Redacted]	[Redacted]	[Redacted]

[REDACTED]	[REDACTED]	[REDACTED]
	[REDACTED]	[REDACTED]

[REDACTED]

[REDACTED]

[REDACTED]

[REDACTED]

[REDACTED]

[REDACTED]

[REDACTED]

[REDACTED]

[REDACTED]

[REDACTED]

**3.9.4.1 Vital Signs**

Vital signs parameters, including blood pressure, temperature, pulse rate and respiration rate, will be obtained according to study schedule procedures. All vital signs parameters (blood pressure, temperature, pulse rate, and respiration rate) will be listed. Abnormal vital sign values will be flagged.

Vital signs parameter values will be collected before, during, and after completion of the IV administration and before and after the completion of the SC administration at each visit. Change from baseline for each vital signs parameter to each scheduled visit will be summarized by treatment group using descriptive statistics. For vital sign assessments collected on the dosing day, the vital sign data will be summarized by time points of interest as well. The time points of interest are as follows:

- pre-dose assessment,
- the 1st set of assessment after dosing, and
- the last set of assessment before discharge from site.

The results for the DB treatment period and the OL treatment period will be presented using the as-treated population and OL population respectively.

### **3.9.4.2 Electrocardiogram**

12-lead Electrocardiogram (ECG) measurements will be performed according to the study schedule. The ECG data will be listed. The overall interpretation of the ECG results (Normal; Abnormal, not Clinically Significant; and Abnormal, Clinically Significant) will be summarized using frequency count and percentages by visit and treatment groups. The results for the DB treatment period and the OL treatment period will be presented separately using the as-treated population and the OL population respectively.

## **3.10 Pharmacokinetics and Immunogenicity**

Serum MEDI2070 concentration data will be summarized descriptively by visit using the PK population. Individual and mean serum concentration-time profiles of MEDI2070 will be generated. PK data obtained in this study will be combined with all available PK data for MEDI2070 and analyzed using population PK methodology and will be reported separately from the CSR for this study.

In addition, the presence of anti-drug antibodies (ADA) to MEDI2070 in serum will be assessed and reported. Immunogenicity results (binding and, if positive, neutralizing) will be summarized by the number and percentage of subjects who develop detectable ADAs. If possible, the relationship between PK and ADA status will be summarized.

## **4 INTERIM ANALYSIS**

An interim analysis may be conducted when at least 75% of the total planned number of subjects has completed the Week 16 visit or withdrawn prior to the Week 16 visit. Data for the primary and secondary endpoints through Week 16 will be analyzed as part of the interim analysis for internal decision making purposes. To ensure the blinding of each subject's treatment assignment throughout the 28-week placebo-controlled, double-blind period, the interim analysis will be conducted by a limited number of sponsor personnel who are not involved in the conduct of the study. Study site personnel and sponsor personnel directly associated with the conduct of this study and the study subjects will remain blinded to the treatment assignment for individual subjects and to the outcome of interim analysis until the completion of the 28-week placebo-controlled, double-blind period.

Since this is a Phase 2b study, the interim analysis is intended to assist internal decision making and does not include a possibility to stop the study for efficacy or futility. Thus, there will be no alpha level adjustment for the final analysis. Should the sponsor choose to perform

[figure not shown]
such an interim analysis, the details would be described in an interim unblinding analysis plan prior to unblinding.

The primary analysis will be performed when all subjects complete the initial 16-week induction period. All the data available by the time of primary analysis database snapshot will be included in the analysis, including available data through Week 28 and the open-label period for a certain proportion of subjects. At the time of the primary analysis, selected personnel from the sponsor will be unblinded to individual treatment assignments as will be outlined in an unblinding plan. Study team members who are unblinded to conduct and review the results from the primary analysis will be removed from the blinded study team and the associated study responsibilities.

A further analysis is planned when all subjects complete the maintenance period, at Week 28. The study will be blinded to all subjects, investigators, and sponsor study team through the end of the maintenance period.

The final analysis for the study, including all study periods and all data, will be performed at the end of the study.

Independent Data Monitoring Committee (IDMC) analysis will be performed for the safety data on a regular basis throughout the DB treatment period of the study as set out in the IDMC charter, i.e. until the last subject completes Week 28. A separate IDMC SAP and/or SPP will be prepared.

## **6 APPENDIX**

### **6.1 CDAI Score**

The CDAI is the oldest and most widely used of several multi-item instruments that have been developed and is validated for use in clinical studies to measure disease activity in CD (Best et al, 1976; Sands et al, 2005). The CDAI measures the severity of active disease using symptom scores that are monitored over the previous week and includes subject-reported symptoms, physician-assessed signs, and laboratory markers.

The CDAI score is calculated by summing weighted scores for subjective items (number of liquid or very soft stools, the degree of abdominal pain over a week (on a scale of 0-3, mild

to severe) and general well-being (on scale of 1-4, “Generally well” to “Terrible”) recorded by a diary during a 1-week period, and objective items (associated symptoms, taking antidiarrheal such as loperamide/opiates, abdominal mass, hematocrit, daily morning temperature, and body weight). The CDAI scores range approximately from 0 to 600, with higher scores indicating greater disease activity (See Table 3.4.1.1-1 for details).

The CDAI will be calculated at the site in order to determine the eligibility for the study. For statistical analysis, CDAI for all visits will be also calculated based on the data entered in the eCRF.

**Table 6.1-1 Items Included in CDAI and Their Weights**

Item	× Weight	Total
Total number of liquid or very soft stools over past week	×2	X 1
Total abdominal pain score (rating: 0-3) over past week (range: 0-21)	×5	X 2
Total general well-being score (rating: 1-4) over past week (range: 1-28)	×7	X 3
Sum of presence of following clinical signs over past week: 1. Arthritis/Arthralgia (1=yes, 0=no) 2. Iritis/ uveitis(1=yes, 0=no) 3. Erythema Nodosum/Pyoderma Gangrenosum/Aphthous Stomatitis (1=yes, 0=no) 4. Anal Fissure, Fistula or Abscess (1=yes, 0=no) 5. Other Fistula (1=yes, 0=no) 6. Fever >37.8 C During Past Week(1=yes, 0=no)	×20	X 4
Antidiarrheal use (Eg, Diphenoxylate hydrochloride) (0=none, 1=yes)	×30	X 5
Abdominal mass (none=0, equivocal=2, present=5)	×10	X 6
Deviation of Hematocrit levels (minimum value = 0) 47 - hematocrit (males) 42 - hematocrit (females)	×6	X 7 (if value<0, enter 0)
Weight ratio 100×(1-[Current body weight / standard weight]) Minimum = -10 for overweight subject Maximum = 10 for underweight subject	×1	X 8 (if value<-10, enter -10, if value >10, enter 10)
CDAI score		$\sum_{i=1}^8 X_i$

In addition, following set of rules will be applied:

- For items 1, 2 and 3, if information is available only for  $\leq 3$  days, then CDAI score will be set to missing. Otherwise, the sub score for each of these three items will be calculated as mean value of item from available days  $\times 7$ .
- For all items, if a subject doesn't have score for any of the sub categories, CDAI score will be set to missing.
- Any total CDAI score  $< 0$  will be considered as 0 in the analysis.

Subjects with scores of  $< 150$ , 150 to 219, and 220 to 450 represent remission, mild disease, and moderate to severe disease, respectively; whereas subjects with scores of  $> 450$  have very severe disease (Buxton et al, 2007).

### **6.3 Covariate-adjusted difference of proportion using logistic regression**

The fitted logistic regression model is used to predict the response rate for every subject in the study as if they had received the treatment or the control intervention, and the difference in the average of the treated and control rates is computed. The delta method is used to calculate a standard error for the difference and an associated CI. Regarding the strata (covariate) values in the trial as a population distribution (e.g. regarding strata frequencies as fixed, which is also implicit in the weighted mean risk difference estimators), the LR estimator is the maximum likelihood estimator of the risk difference under the logistic model (See the SPP for pseudo SAS codes).

### **6.4 Visual acuity notation conversions**

The visual acuity notation routinely used at different sites may vary. Each site should convert the acuity notation to decimal format to enter onto the electronic case report form (eCRF).
